Evaluation of the Effectiveness of Vestibular Rehabilitation With Virtual Reality Systems in Individuals With Visually Induced Motion Sickness

NCT: Pending

Document Date:
June 2025

Study Protocol

A test protocol was developed to provide vestibular rehabilitation using virtual reality systems for individuals with visually induced motion sickness (VIMS).

The study protocol consists of three phases:

In the first phase, all participants underwent the Simulator Sickness Questionnaire (SSQ) and static posturography tests, including Balance Screening and Limit of Stability assessments, prior to the initial evaluation. Subsequently, participants were exposed to 5 - minute YouTube open-access 360° virtual reality (VR) videos with varying difficulty levels determined beforehand. The initial evaluation lasted 30 minutes and was structured as follows: 5 minutes of easy stimulation followed by 5 minutes of rest, 5 minutes of moderate stimulation followed by 5 minutes of rest, and 5 minutes of high stimulation followed by 5 minutes of rest. During each 5-minute stimulation, heart rate and balance screening tests were measured at minutes 1, 3, and 5. After the total 15 minutes of stimulation, final measurements including the SSQ, balance screening, and Limit of Stability tests were repeated (Table 1).

Table 1 Phase I: Initial Evaluation Protocol

Phase I	Easy Level	Moderate Level	High Level
Stimulus			
Pre-stimulation	Walking Video Simulator Sickness Questionnaire (SSQ) Balance Screening Limit of Stability	Driving Video Simulator Sickness Questionnaire (SSQ) Balance Screening Limit of Stability	Drone Video Simulator Sickness Questionnaire (SSQ) Balance Screening Limit of Stability
Order of Stimulation	During each 5-minute stimulation, Balance Screening (BS) and heart rate measurements were taken at minutes 1, 3, and 5.	During each 5-minute stimulation, Balance Screening (BS) and heart rate measurements were taken at minutes 1, 3, and 5.	During each 5-minute stimulation, Balance Screening (BS) and heart rate measurements were taken at minutes 1, 3, and 5.
Post-stimulation	Simulator Sickness Questionnaire (SSQ) Balance Screening Limit of Stability	SSQ	SSQ
Qualitative Data Collection Tool	SSQ	SSQ	SSQ

Quantitative Data Collection Tool	Balance Screening Heart Rate Monitor	Balance Screening Heart Rate Monitor	Balance Screening Heart Rate Monitor
-----------------------------------	---	---	---

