In the second phase, a four-week rehabilitation program was designed for individuals with VIMS, consisting of two 1-hour sessions per week (Table 2). The prepared rehabilitation program was administered to the study group using virtual reality systems.

Table 2 4-week rehabilitation program

	Seans	Seans
Two sessions per week	6 × 5-minute easy stimulations (with 5-minute rest periods between stimulations)	4 × 5-minute easy stimulations plus 2 × 5-minute moderate stimulations (with 5-minute rest periods between stimulations)
Two sessions per week	6 × 5-minute moderate stimulations (with 5-minute rest periods between stimulations)	2 × 5-minute easy stimulations plus 4 × 5-minute moderate stimulations (with 5-minute rest periods between stimulations)
Two sessions per week	6 × 5-minute moderate stimulations (with 5-minute rest periods between stimulations)	3 × 5-minute moderate stimulations plus 3 × 5-minute high stimulations (with 5-minute rest periods between stimulations)
Two sessions per week	6 × 5-minute high stimulations (with 5-minute rest periods between stimulations)	30-minute final evaluation session: 1 × 5-minute easy stimulation + 2 × 5-minute moderate stimulations + 3 × 5-minute high stimulations

In the third phase, following the rehabilitation program, participants were reassessed using the Simulator Sickness Questionnaire (SSQ), and static posturography tests, including Balance Screening and Limit of Stability assessments, were repeated.

Statistical Analysis

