The data obtained in this study were analyzed using Statistical Package for Social Sciences (SPSS) for Windows, version 25.0. Descriptive statistical methods (number, percentage, minimum-maximum values, mean, and standard deviation) were used to summarize the data. The normality of the data was assessed using skewness and kurtosis values. For normally distributed data, independent-samples t-tests were used to compare quantitative variables between two independent groups, and paired-samples t-tests were used to compare two dependent groups. Pearson correlation was applied to examine relationships between numerical variables. For data that were not normally distributed, the Friedman test was used for comparisons of more than two dependent groups. When a significant difference was found, the adjusted Bonferroni test was used to identify the group causing the difference. Spearman correlation was used to assess relationships between numerical variables. The homogeneity of categorical variables was examined using the Chi-square test.

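### No primary outcome, alpha or list of comparisons is stated, and the only multiplicity correction does not reach the tests of three unranked Phase III outcomes

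*Combined protocol and SAP*

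**What the plan says.** The Statistical Analysis section lists tests by type of data. Where normality is accepted, the between-group rule is that "independent-samples t-tests were used to compare quantitative variables between two independent groups". Within-group comparisons get a separate rule, namely that "paired-samples t-tests were used to compare two dependent groups". Non-normal data with three or more related measurements go to the Friedman test, and the sentence after that gives the plan's one correction: "When a significant difference was found, the adjusted Bonferroni test was used to identify the group causing the difference". Pearson and Spearman correlations and a chi-square test complete the list. The section gives no primary outcome, alpha or sidedness, and does not say which outcomes are compared at which time.

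In the Study Protocol, the first phase says that "all participants underwent the Simulator Sickness Questionnaire (SSQ) and static posturography tests" at the outset. In the second phase, "The prepared rehabilitation program was administered to the study group using virtual reality systems". In the third phase, "participants were reassessed using the Simulator Sickness Questionnaire (SSQ), and static posturography tests, including Balance Screening and Limit of Stability assessments, were repeated". None of the three Phase III measures is marked as more important than the others. A second group appears only by implication, in the reference to two independent groups. Its membership, how it was formed and whether it was reassessed are not described.

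**The concern.** The title promises an evaluation of effectiveness, but the plan does not say which result decides it. With three unranked outcomes, each can support the claim, and several chances at a claim carry a higher false-positive risk than one.

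The Bonferroni sentence could be taken for overall multiplicity control. It is not. It locates a difference within one set of repeated measurements after a significant Friedman test. It does not adjust across outcomes and does not apply to either t-test. A reader of the results could not tell a planned finding from the best of three.

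**Working it through.** The documents state no alpha, power or sample size, so there is no planned figure to reproduce. The calculation shows what three uncorrected tests would do under stated assumptions.

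**Input from the documents**
- Three Phase III outcomes, unranked, with no correction across them (third phase; Statistical Analysis).

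**Assumptions, none given in the documents**
- Two-sided 5% per test, so 2.5% in the favourable direction and critical value c = 1.96.
- One roughly normal score, and one test, per outcome.
- Both groups reassessed in Phase III, with equal expected values if there is no treatment effect.
- A common correlation ρ between the test statistics, from 0 to 0.9.

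**Correlation 0**
- Favourable: 1 − (1 − 0.025)³ = 1 − 0.9269 = 0.0731.
- Either direction: 1 − (1 − 0.05)³ = 1 − 0.8574 = 0.1426.

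**Correlation above 0**
- Favourable: 1 − ∫ φ(u) [Φ((c − √ρ·u)/√(1−ρ))]³ du.
- Either direction: replace the bracket by Φ((c − √ρ·u)/√(1−ρ)) − Φ((−c − √ρ·u)/√(1−ρ)).

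**Holm across three.** If no outcome has an effect, Holm makes a false claim only when the smallest p-value is at or below 0.05/3 = 0.0167. At correlation 0 this gives 1 − (1 − 0.0167)³ = 0.0492.

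| Correlation | Favourable, uncorrected | Either direction, uncorrected | Either direction, Holm |
|---|---|---|---|
| 0 | 7.3% | 14.3% | 4.9% |
| 0.5 | 6.3% | 12.5% | 4.5% |
| 0.7 | 5.5% | 10.9% | 3.9% |
| 0.9 | 4.2% | 8.4% | 3.0% |
| One test only | 2.5% | 5% | – |

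The favourable rate is 7.3/2.5 = 2.9 times the single-test rate at correlation 0, and 4.2/2.5 = 1.7 times at 0.9.

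**Small-sample check.** Simulated two-sample t-tests with an assumed 10, 15, 20 or 30 per group (400,000 replicates each) gave favourable rates of 7.3% at correlation 0, 6.3–6.4% at 0.5 and 4.2–4.3% at 0.9. The unknown sample size therefore hardly matters to the error rate.

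**If only the study group was reassessed.** The same figures apply to three paired tests when there is no mean change, with ρ taken between the change scores.

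**The case against.** The strongest objection is that the percentages rest on a comparator that the documents do not describe. No method of forming the groups is given. The second group could be untreated people with VIMS or people without it, and the independent-samples tests could concern Phase I only. If the groups differ by nature, a Phase III difference is expected whatever rehabilitation does, and neither 2.5% nor 4.2–7.3% describes the error. This stands. The figures are an illustration, and the second group must be defined before any between-group test is offered as evidence of effectiveness.

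It can also be said that the t-tests apply only to normally distributed data, so three t-tests may not occur. This stands as a limit on the figures but not as a defence: three uncorrected tests of another kind raise the same problem.

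Three stronger readings are tempting and should not be drawn:
- *That this trial's false-claim rate is 4.2–7.3%.* Alpha, sidedness, correlation, comparability and one score per outcome are all assumed.
- *That the SSQ is excluded from the t-tests because Table 1 lists it under "Qualitative Data Collection Tool".* That row describes Phase I only and may be loose wording for a questionnaire. The matching quantitative row omits Limit of Stability as well, so the table cannot settle which Phase III outcomes are tested.
- *That no primary outcome was ever chosen.* The trial number is shown as pending, and these documents show only that none is stated here.

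**Conclusion.** The gap is certain: there is no primary outcome, no alpha, no list of comparisons, and no correction that reaches the t-tests on the three unranked Phase III outcomes. Its size is conditional. Under the assumptions set out above, at least one false favourable result has a chance of 4.2–7.3% instead of 2.5%, and a false result in either direction 8.4–14.3% instead of 5%. The essential assumption is that the groups would be equal in Phase III absent a treatment effect, and the documents neither support nor exclude it. Heart rate, the readings at minutes 1, 3 and 5, paired tests and correlations would add further chances if they too were used to claim effectiveness. The point should be corrected because a better analysis is available from measurements already described.

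**What to change.** In the Statistical Analysis section:

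1. State who the second group is, how it was formed and whether it was reassessed in Phase III.
2. State a two-sided alpha of 5%.
3. If the second group is a comparable untreated VIMS group reassessed in Phase III, apply Holm (0.0167, 0.025, 0.05) across the three between-group Phase III comparisons. Adjust each for the Phase I pre-stimulation value of the same measure. Fix that time point now as the value taken before any stimulation. Phase I also has post-stimulation values, and a baseline picked after seeing results is a choice that Holm does not control.
4. If outcome data have not been seen, an alternative is one pre-named primary (SSQ) at 5%, with Holm (0.025, 0.05) on the other two only if it is significant. The past tense ("The data obtained in this study were analyzed") suggests, without proving, that data have been seen. In that case label any primary as post hoc.
5. If the second group is not comparable or was not reassessed, apply Holm to the three paired study-group tests and limit the conclusion to within-group change.
6. Report all other tests as exploratory, with estimates and confidence intervals.

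**Cost.** No new measurements are needed, only re-analysis. If there is no comparable reassessed group, however, the data described cannot support a between-group effectiveness claim. Power per outcome falls. An outcome with 80% power at 5% has Φ(2.802 − 2.394) = 66% at the first Holm step, or about 75% over the full procedure if all three outcomes have that power and are independent. Under the alternative in item 4, the primary keeps its power. A secondary with 80% power at 5% has Φ(2.802 − 2.241) = 71% at its first Holm step, hence 0.80 × 0.71 = 57% after a primary with 80% power, if the outcomes are independent. The 80% is assumed, as the documents give no sample size.

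### Holm's step-down adjustment would be a cheap, slightly more powerful replacement for single-step Bonferroni after the Friedman test; the planned method is valid as it stands

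*Combined protocol and SAP*

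**What the plan says.** The Statistical Analysis section states: "For data that were not normally distributed, the Friedman test was used for comparisons of more than two dependent groups". It continues: "When a significant difference was found, the adjusted Bonferroni test was used to identify the group causing the difference". So pairs are examined only after a significant Friedman result, and a Bonferroni-type adjustment is then applied.

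The section does not give the significance level, the pairwise test, the number of comparisons in a family, or the series to which Friedman is applied. The account of the first phase in the Study Protocol suggests candidates. There are three difficulty levels (easy, moderate, high), and within each level: "During each 5-minute stimulation, heart rate and balance screening tests were measured at minutes 1, 3, and 5". Families of three conditions are therefore plausible, but a nine-cell level-by-minute analysis is not excluded.

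**The concern.** Single-step Bonferroni holds every pair to the strictest threshold, even after other pairs have been shown to differ. Once one pair is rejected, fewer null hypotheses can still be true, and the remaining pairs could be tested less severely without raising the ceiling on family-wise error. Bonferroni does not use this.

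What is at stake is power, not validity. Where a Friedman test finds a difference among levels or minutes, the plan has a somewhat lower chance than necessary of saying where it lies. Neighbouring conditions are affected most, because their differences are likely to be the smallest.

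**Working it through.** The plan states no power, sample size or significance level, so there is no figure of its own to reproduce.

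**Inputs.** From the documents: Friedman first, then a Bonferroni-type step; three levels and three minutes in the first phase. Assumed: two-sided 5%; ordinary Bonferroni as the meaning of the follow-up; 20 or 30 participants; three conditions 0.6 residual SD apart.

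**1. Thresholds for three conditions.** There are 3 × 2 / 2 = 3 pairs.
- Bonferroni: every p-value is compared with 0.05/3 = 0.0167.
- Holm: the smallest is compared with 0.05/3 = 0.0167, the next with 0.05/2 = 0.025 and the last with 0.05/1 = 0.05, stopping at the first failure.

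**2. Holm rejects at least as often.** With m pairs, suppose a p-value is at or below 0.05/m. Every smaller p-value is too, and each of Holm's thresholds is at least 0.05/m, so Holm also rejects it. Requiring a significant Friedman test first affects both rules alike, so the ordering stays.

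**3. The ceiling is the same.** If m0 null hypotheses are true, the first of them that Holm reaches is tested at no more than 0.05/m0. The chance that any of m0 true nulls passes that threshold is at most m0 × 0.05/m0 = 0.05. The Friedman requirement can only remove rejections. The argument needs valid pairwise p-values and holds for any number of conditions, including nine cells (9 × 8 / 2 = 36 pairs).

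**4. What the divisor costs one pair.** Take a pair with 80% power at 5%, so that the mean of its z-statistic is 1.960 + 0.842 = 2.802.
- At 0.0167: P(Z > 2.394 − 2.802) = 66%.
- At 0.025: P(Z > 2.241 − 2.802) = 71%.
- At 0.05: 80%.

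Bonferroni always leaves this pair at the first line. Holm moves it to the second or third once other pairs are rejected.

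**5. Simulated gain.** Chance of detecting one adjacent pair, with Friedman required first, Wilcoxon signed-rank tests and normal errors:

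| Participants | Bonferroni | Holm | Gain (points) |
|---|---|---|---|
| 20 | about 24% | 31–32% | 7–8 |
| 30 | about 40% | 51–52% | 11–12 |

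Across Wilcoxon and rank-mean z comparisons, and normal and skewed errors, the gain was about 4 to 14 points. The low end came from rank-mean z tests at 20 participants. Averaged over all three pairs the gain is smaller. With 20 participants, within-person correlation 0.5 and shifts of 0, 0.4 and 0.8 SD, rank-mean z power went from 0.31 to 0.33. In the same setting, Wilcoxon power without the Friedman requirement went from 0.388 to 0.437.

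**6. Actual error (Wilcoxon, three conditions).** With all conditions equal, Holm makes a false rejection exactly when Bonferroni does, because the first threshold is shared: about 2.0–2.6% after a significant Friedman test. With one condition far from two equal ones, Bonferroni ran at 1.3–1.6% and Holm at 4.7–5.1%. The simulation standard error is about √(0.05 × 0.95 / 20,000) = 0.15 points, so 5.1% is compatible with 5%.

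**The case against.** The strongest reply is that nothing is broken. The planned rule is valid and conservative, and preferring Holm is a choice of efficiency. That stands. Four further points also have force.

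- **The reading is not certain.** The follow-up is called an adjusted Bonferroni test, with no divisor or pairwise statistic. If a stepwise version was meant, the gain shrinks or disappears and only the wording needs repair.
- **Error is spent, not saved.** The ceiling is unchanged but the actual rate can rise towards it, as step 6 shows. Holm does not find more at the same actual error.
- **The plan as a whole is not too strict.** It states no control across outcomes or families. Two measures (heart rate, balance screening) in each of three levels make 2 × 3 = 6 possible three-minute families. At 5% each and if independent, the chance of at least one false Friedman result is 1 − 0.95^6 = 26%. A reader might infer over-control of the whole analysis; the documents do not support that.
- **The branch is peripheral.** The two-group and two-occasion t-tests are untouched.

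A reader might also infer that, with three conditions, pairs could be tested at an unadjusted 5% after a significant Friedman test, since at most one pair can then still be equal. The logic is sound for exactly three conditions with valid tests, but the documents do not say that the families have three conditions. With four, unadjusted Wilcoxon tests gave family-wise error of 12–13%; with nine cells, unadjusted tests gave 36–55%. Even with three, rank-mean z tests reached about 6%. In a plan without control across outcomes, that shortcut should not be adopted.

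Nor should the gain be read as 14% rising to about 40% at 20 participants. That contrast drops the adjustment and also changes the pairwise test from rank-mean z to Wilcoxon.

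**Conclusion.** The point holds as a minor improvement, not as an error. If the follow-up is ordinary Bonferroni, Holm applied to the same p-values has the same family-wise ceiling in each Friedman family and is never less powerful. This conclusion does not depend on sample size, effect size or number of conditions.

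The size does depend on them. The 4 to 14 points for an adjacent pair rest on an assumed two-sided 5% level, 20 to 30 participants and three conditions 0.6 SD apart. They are not bounds: the gain falls towards zero when power is very low or near 1, and it varies with the shape of the errors. The documents do not show that any real difference would be missed, because they give none of the figures needed to tell.

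**What to change.** Replace the follow-up sentence in the Statistical Analysis section with:

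> When the Friedman test is significant, all pairs of conditions are compared and the pairwise p-values are Holm-adjusted within that Friedman family.

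Keep whichever pairwise test the plan already uses, and name it. State the significance level and list the Friedman families (levels, minutes or level-by-minute cells). Do not add an unadjusted 5% rule for three conditions.

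The cost is small. No new data or tests are needed, and the adjustment can be done by hand: for three pairs, multiply the ordered p-values by 3, 2 and 1, and let no adjusted value fall below the one before it. Holm gives no simple simultaneous confidence intervals, but the plan states none. Actual family-wise error will move closer to the nominal level.

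The section is written in the past tense. If the analysis has been run, moving to a less strict rule should be reported as post hoc, with the Bonferroni results shown alongside.
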